- A mean-centering Partial Least Squares analysis will show a group (psilocybin vs placebo) × condition (alcohol vs neutral) interaction, in the anterior cingulate cortex, insula, striatum, and frontal gyrus where the neural differentiation between alcohol and neutral cues will differ between psilocybin and placebo groups, with reduced differentiation in the psilocybin group. Additionally, in-scan craving ratings following viewing pictures of alcohol (VAS 0-100) will be lower in participants randomized to psilocybin relative to placebo.
- At Week 1, resting-state functional connectivity, defined as Fisher r to z -transformed correlations between BOLD time series extracted from the striatum (defined using the Tian subcortical atlas) and pre-specified regions of the salience network (defined using the Schaefer/Yeo cortical atlas), will differ between participants randomized to psilocybin and placebo.

- **Exploratory hypotheses:**

- Lower Week-1 neural differentiation between alcohol and neutral cues (lower latent variable scores from a separate single-group Partial Least Squares analysis collapsing across treatment groups) will be associated with greater reductions in alcohol consumption from baseline to Week 12. Differences between psilocybin and placebo

groups in striatal functional connectivity (striatum-salience network and striatum-prefrontal) at Week 1 will be associated with changes in alcohol consumption from baseline to Week 12.

- Resting-state functional connectivity in the Control networks (defined using the Schaefer/Yeo cortical atlas) will be lower in the psilocybin group compared to the placebo group at Week 1 and will be associated with changes in alcohol consumption from baseline to Week 12.
- Greater acute subjective effects measured on the dosing day will be associated with greater reductions in alcohol consumption from baseline to Week 12.
- At Week 1, resting-state functional connectivity, defined as Fisher r to z -transformed correlations between BOLD time series extracted from the striatum (defined using the Tian subcortical atlas) and all brain regions (defined using the Schaefer/Yeo cortical atlas), will differ between participants randomized to psilocybin and placebo. Results will be presented as effect sizes i.e., Cohen's D , and inferential statistics i.e., p -values will not be reported.

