- Task-based fMRI analyses will be repeated using a GLM in SPM to provide a map of task response as well as group-level effects on the task response.

STUDY METHODS

STUDY DESIGN

The QTT trial was a randomized, double-blinded, placebo-controlled, parallel-group, single-site clinical trial for 12 weeks (main trial) and a long-term follow-up 26 weeks after the intervention. The trial compared single-dose psilocybin therapy vs placebo therapy. The treatment involved two preparation sessions, a high-dose psilocybin session (25 mg) or placebo (inert substance) session, and three integration sessions. Baseline data was collected at screening visit and outcomes were assessed 1, 4, 8, 12 (primary endpoint) and 26 weeks after the psilocybin/placebo session. A sub-group of participants underwent fMRI scan 1 week after the intervention (no baseline scan).

RANDOMIZATION

The participants were randomized in two groups (1:1): psilocybin therapy or placebo therapy. The randomization was stratified in terms of age (20-45, 46-70 years), sex, and baseline alcohol consumption i.e. the number of heavy drinking days in the last 28 days before inclusion measured by the TLFB-method (5-15, 16-28 days). The randomization tool in REDCap was used. Patients, investigators, other caregivers performing assessments, and persons performing data analysis have been blinded from the time of randomization and until the time of database unlock.

SAMPLE SIZE

The study was initially designed to enroll 90 participants, based on an a priori power analysis informed by effect sizes reported in the open-label pilot study by Bogenschutz and colleagues (2015). Assuming a two-

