sided alpha level of 0.05 and 90% power, the required sample size was estimated to be 27 participants per treatment arm. Anticipating a dropout rate of approximately 40%, the total planned enrollment was therefore set at 90 participants. Due to delays associated with the COVID-19 pandemic and lack of financial resources to continue the study, recruitment was terminated before reaching the intended enrollment target. Following the decision to stop recruitment, a revised power calculation—based on the originally specified primary endpoint and the same effect size assumptions as the initial power analysis—indicated that 22 participants per treatment arm would provide approximately 85% power, corresponding to a total of 44 completers. As of December 2025, the observed dropout rate was substantially lower than anticipated (13%), resulting in 59 enrolled participants, of whom 51 completed the primary endpoint assessment. The number of completers therefore exceeded the minimum sample size required according to the revised power calculation. Of these, 28 completed fMRI scans, however only those with complete behavioural data and adequate quality imaging data for analyses will be retained for analyses. Imaging data will be quality controlled using fMRIPrep.

TRIAL POPULATION

Recruitment

Recruitment began September 2023 and ended September 2025. Last patient's last visit in the main trial i.e., the 12-week outcome assessment was on 22nd December 2025. Last patient's last visit concluding the entire study i.e., the 26-week follow-up will be end of March 2026. Participants were recruited in part from outpatient clinics, but predominantly from society via advertisement.

Eligibility

Treatment seeking individuals aged 20-70, weighing 60-95kg, diagnosed with AUD and alcohol dependence according to DSM-V and ICD-10, respectively, who had at least 5 heavy drinking days within the past 28 days of screening, and no co-occurring substance use disorders (except nicotine) and no concomitant pharmacotherapy for AUD.

OUTCOMES

OUTCOME CATEGORY	SOURCE	TIME POINTS	PRIMARY COMPARISON (BETWEEN-GROUP DIFFERENCE)
Primary			
1. Percentage of Heavy Drinking Days (PHDD)	TLFB/28 days	BL, W4, W8, W12	W12, adjusted for BL
Secondary			
2. Alcohol consumption:			
• % drinking days	TLFB/28 days	BL, W4, W8, W12	W12, adjusted for BL
• Drinks per day	TLFB/28 days	BL, W4, W8, W12	W12, adjusted for BL
• Drinks per drinking day	TLFB/28 days	BL, W4, W8, W12	W12, adjusted for BL

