Analyses will examine associations between selected secondary endpoints and the primary endpoint. These analyses are intended to assess relationships between outcomes and to inform hypotheses regarding potential mechanisms of action. Associations will be evaluated using correlation analyses and/or regression models as appropriate, without adjustment for multiplicity.

- Week 1 neural differentiation between alcohol and neutral cues, quantified using latent variable scores from a mean-centering Partial Least Squares (PLS) analysis of whole-brain blood oxygenation level-dependent (BOLD) responses, and associations with subsequent changes in alcohol consumption and brain-derived neurotrophic factor (BDNF) levels. Resting-state functional connectivity at Week 1 (striatum to salience-network, and within control-network connectivity) and their associations with changes in alcohol consumption and changes in BDNF levels.
- Acute subjective effects during the dosing session and their associations with changes in alcohol consumption and changes in BDNF levels.

Significance level

The primary endpoint will be tested using a one-sided significance level of 0.05 with corresponding 95% confidence intervals, reflecting an a priori directional hypothesis that psilocybin will reduce heavy drinking days compared with placebo. The direction of the primary hypothesis and the use of one-sided testing were prespecified prior to database lock and unblinding and were informed by consistent evidence from prior

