clinical studies. Effects in the opposite direction, if observed, will be fully reported and interpreted descriptively. All secondary and exploratory analyses will be conducted using two-sided significance tests. For Partial Least Squares fMRI analyses, latent variable significance will be assessed via permutation testing (1,000 permutations, $p < 0.05$), with voxel reliability determined by bootstrap ratios $\geq |2.5|$ (200 bootstrap iterations). The PLS analysis will include group (psilocybin vs placebo) as a between-subjects factor, testing for group \times condition (alcohol vs neutral) interactions in whole-brain BOLD responses. Additionally, a separate single-group PLS analysis (collapsing across psilocybin and placebo groups) will be performed to derive individual latent variable scores reflecting each participant's neural differentiation between alcohol and neutral cues. These individual LV scores will be correlated with changes in alcohol consumption from baseline to Week 12. No multiplicity adjustments will be performed, and no additional covariate adjustments will be applied except for the baseline value of the endpoint in question.

Statistical software

All statistical analysis will be performed with R. fMRI data will be preprocessed using fMRIPrep v25.1.0 (<https://fmriprep.org/en/stable/>) and denoised using Nilearn in Python. Partial Least Squares analyses are performed using the Rotman-Baycrest PLS Toolbox in MATLAB. Resting-state functional connectivity analyses will be performed using custom code in MATLAB.

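### The SAP's covariate rule leaves no room for a head-motion sensitivity analysis of the Week 1 resting-state connectivity results

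*SAP*

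**What the plan says.** The last sentence under Significance level, in the same paragraph as the fMRI tests, states that "no additional covariate adjustments will be applied except for the baseline value of the endpoint in question". It makes no exception for imaging.

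Study design records that "A sub-group of participants underwent fMRI scan 1 week after the intervention (no baseline scan", and the Outcomes table lists both imaging endpoints as Week 1, post-treatment only. The one permitted covariate therefore does not exist for connectivity. In the associations with drinking, at most the drinking baseline could enter.

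The analyses affected are:
- the secondary hypothesis that Week 1 striatum-salience connectivity "will differ between participants randomized to psilocybin and placebo";
- the exploratory control-network comparison and the exploratory striatum-to-all-regions comparison, the latter reported as effect sizes without p-values;
- the associations of Week 1 connectivity with change in alcohol consumption, listed under Hypotheses and under Pre-specified mechanistic/exploratory analyses.

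Motion can be dealt with before the group models. Sample size says "Of these, 28 completed fMRI scans, however only those with complete behavioural data and adequate quality imaging data for analyses will be retained", and then "Imaging data will be quality controlled using fMRIPrep". Statistical software says "fMRI data will be preprocessed using fMRIPrep v25.1.0" and that the data are "denoised using Nilearn in Python". The SAP does not mention head motion by name. Its only sensitivity provision specific to neuroimaging is restriction to complete cases, and the Efficacy analyses section allows alternative models only when model assumptions fail.

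**The concern.** Connectivity here is a correlation between BOLD time series, which in-scanner movement can shift. Quality control and denoising act within each scan, and some motion may remain. A group-level covariate is the usual check on that remainder, and the rule closes it off.

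Two separate distortions are possible:
- **Arm comparison.** If residual motion differs systematically between arms, part of that difference appears as a difference in connectivity. This could arise if treatment changed movement at Week 1, or if selection into the scanned and quality-passed subset differed by arm.
- **Association with drinking.** If residual motion is related to both connectivity and drinking change, it creates a correlation between them with no direct link. Randomisation gives no protection here.

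At stake are one secondary endpoint and several exploratory ones. The primary result is not affected. The timing matters: a motion-adjusted model added after the results are seen would be post hoc and contrary to the SAP.

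**Working it through.** **The plan's own figures.** The SAP gives no motion figure and no power or sample-size calculation for imaging; its Sample size figures concern the primary endpoint. There is nothing to reproduce on this point.

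**Inputs**
- From the SAP: at most 28 scans, no baseline scan, two-sided tests for secondary and exploratory analyses.
- Assumed: 14 scans per arm (the split is not given), a 5% level for the connectivity tests, no true effect, and the motion parameters below.

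**Arm comparison.** Let r be the correlation of residual motion with connectivity within arm and dm the systematic arm difference in motion, in SD units. The spurious shift in connectivity is r × dm SD. With 14 per arm the t statistic has 26 degrees of freedom and noncentrality r × dm × √(14/2). The largest case is 0.5 × 0.8 = 0.40 SD, noncentrality 0.40 × 2.646 = 1.058.

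| r | dm | Shift (SD) | Unadjusted rejection |
|---|---|---|---|
| any | 0 | 0 | 5.0% |
| 0.2 | 0.5 | 0.10 | 5.7% |
| 0.3 | 0.5 | 0.15 | 6.7% |
| 0.3 | 0.8 | 0.24 | 9.4% |
| 0.5 | 0.5 | 0.25 | 9.8% |
| 0.5 | 0.8 | 0.40 | 17.5% |

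Simulation of the r = 0.3 and r = 0.5 settings agrees with the unadjusted column to within a percentage point. With motion in the model the simulated rejection rate is 4.4% to 5.4%.

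**Chance imbalance is not the problem.** The standard error of a chance arm difference in motion is √(2/14) = 0.38 SD, so visible imbalances will occur. They are already inside the nominal 5%, as the dm = 0 row shows. Only a systematic difference inflates the error.

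**Association.** If motion correlates a with connectivity and b with drinking change, and nothing else links them, the spurious correlation is a × b. By Fisher's z with n = 28, the test statistic is shifted by atanh(a × b) × √25.

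| a | b | a × b | Rejection |
|---|---|---|---|
| 0.3 | 0.2 | 0.06 | 6.0% |
| 0.3 | 0.3 | 0.09 | 7.4% |
| 0.5 | 0.4 | 0.20 | 17.3% |
| 0.5 | 0.5 | 0.25 | 24.8% |

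For a = 0.5 and b = 0.4: atanh(0.20) = 0.203, and 0.203 × 5 = 1.01.

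**Precision.** If motion does not differ by arm, adjustment still removes a share r² of the residual variance: 0.3² = 9% to 0.5² = 25%, for one degree of freedom.

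**The case against.** The strongest reply has four parts.

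1. **Motion is not ignored.** Scans of inadequate quality are dropped and the data are denoised before any group model. This stands: only the remainder is exposed. That the SAP names no motion threshold or confound set is not counted against it, since such detail may sit in the protocol. The point rests on a rule the SAP does state.
2. **The harm is hypothetical.** The documents do not show that motion differs by arm, that it tracks drinking, or how strongly it correlates with connectivity after denoising. This also stands, and it makes every figure above conditional.
3. **Motion at Week 1 is a post-randomisation variable.** If treatment changes it, conditioning on it may remove part of a real effect, and keeping the planned comparison free of such covariates is defensible. This stands as a reason to leave the unadjusted analysis as the main one. It is not a reason to bar a sensitivity analysis.
4. **The rule does not prevent tabulating motion by arm.** Correct, but a table alone does not show how far the estimate moves.

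A reader might infer more than the documents support. Motion that merely tracks drinking would not pass for a psilocybin effect on connectivity: it would distort the connectivity-drinking association, and only motion that differs by arm distorts the treatment comparison. Nor should a difference that loses significance on adjustment be disallowed as a treatment effect. In simulations with 14 per arm, a true direct effect of 0.8 SD and an arm difference in motion of 0.5 to 0.8 SD, such a veto discarded 12% to 21% of significant true results when motion was unrelated to connectivity, and 24% to 36% when the correlation was 0.3.

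**Conclusion.** The point holds as a modest one. The rule is explicit and unqualified, its single exception is empty for connectivity, and no other part of the SAP restores a motion-adjusted check. Under the assumptions of 14 scans per arm and no true effect, false rejection in the arm comparison would be about 7% to 17% for motion differences of 0.5 to 0.8 SD and correlations of 0.3 to 0.5. It stays at 5% if motion does not differ systematically by arm. For the associations it would be about 6% to 17% when motion correlates 0.3 to 0.5 with connectivity and 0.2 to 0.4 with drinking change. For the striatum-to-all-regions analysis the risk is a biased effect size, since no test is reported.

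The documents do not show that such bias is present. What they show is that the plan, as written, would not allow adjustment for it. This is a cheap improvement to secondary and exploratory imaging analyses.

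**What to change.** Amend the covariate sentence under Significance level so that head motion is exempt for the resting-state analyses, as a prespecified sensitivity analysis only:

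- Keep the planned unadjusted comparison or association as the main result.
- Beside it, report the same model with each participant's mean framewise displacement as a covariate.
- Report mean framewise displacement by arm.
- State that where the estimate changes materially on adjustment, the result will be interpreted cautiously. Do not make the interpretation depend on whether significance is kept.

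The change should be made before unblinding. It costs a short addition to the SAP and one extra model per analysis, using a motion measure obtained in preprocessing. The statistical downside is one degree of freedom and the possibility that adjustment for a post-randomisation variable removes part of a real effect, which is why it sits beside the planned result and does not replace it.
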